8.3.5 Severity of Adverse Event or Suspected Adverse Drug Reaction

Adverse events and suspected ADRs (i.e., potentially drug related AEs) will be classified depending on their severity according to the following definitions:

Mild: an AE which is well tolerated by the subject, causing minimum degree of malaise and without affecting normal activities.

GRIFOLS Bioscience Industrial Group	Number	Big-CL-PRT-000020	Version	4.0	Status	Effective	Effective Date	19-Jul-2021	Page	59 of 91
	GC2007 - A Multicenter, Randomized, Open-label Parallel Group Pilot Study to Evaluate Safety and Efficacy of High Dose Intravenous Immune Globulin (IVIG) plus Standard Medical Treatment (SMT) alone in									

Moderate: an AE that interferes with the subject's normal activities.

Severe: an AE that prevents the subject from performing their normal activities.

This category is further subdivided into Grade 3-5 AEs defined according to CTCAE criteria, US Department of Health and Human Services, NIH, and NCI.

Adverse events and suspected ADR severity gradation must be distinguished from AE and suspected ADR seriousness gradation, which is defined according to event consequence. For example, headache can be mild, moderate or severe but not necessarily serious in all these cases.

The investigator will be responsible for assessing the AE and suspected ADR intensity during the clinical trial, taking into account current criteria included in this section.

8.3.6 Expectedness of Adverse Event or Suspected Adverse Drug Reaction (Reference Safety Information)

An AE or suspected ADR (ie, potentially drug related AE) is considered “unexpected” if the nature, seriousness, severity or outcome of the reaction(s) is not consistent with the reference information, which is the Gamunex-C prescribing information and the IB. The expectedness shall be determined by the sponsor for any serious ADRs (potentially related SAEs) according to the reference document for expedited safety reporting purposes.

8.3.7 Seriousness of Adverse Event or Suspected Adverse Drug Reaction

An AE or suspected ADR (ie, potentially drug related AE) is considered “serious” if, in the view of either the investigator or sponsor, it results in any of the following outcomes:

- Death
- Life-threatening AE (life-threatening in the definition of “serious” refers to an event in which the subject was at risk of death at the time of the event; it does not refer to an event which hypothetically might have caused death if it were more severe)
- In-patient hospitalization or prolongation of existing hospitalization*
- A persistent or significant incapacity or substantial disruption of the ability to conduct normal life functions
- A congenital anomaly/birth defect
- An important medical event (important medical event in the definition of “serious” refers to those events which may not be immediately life-threatening, or result in death, or hospitalization, but from medical and scientific judgment may jeopardize the subject or/and may require medical or surgical intervention to prevent one of the other outcomes listed above).

*Hospitalization is to be considered only hospital admission (including emergency room stay) for equal or more than 24 hours. The following hospitalizations should not be reported as SAEs:

GRIFOLS Bioscience Industrial Group	Number	BLG-CL-PRT-000020	Version	4.0	Status	Effective	Effective Date	19-Jul-2021
	GC2007 - A Multicenter, Randomized, Open-label Parallel Group Pilot Study to Evaluate Safety and Efficacy of High Dose Intravenous Immune Globulin (IVIG) plus Standard Medical Treatment (SMT) alone in						Page	60 of 91

- Hospitalization or prolongation of hospitalization needed for procedures required by the clinical trial protocol or as part of a routine procedure followed by the center.
- Admissions not associated with an AE (e.g., social hospitalization for the purpose of respite care, survey visits, or annual physicals).
- Elective or pre-planned hospitalizations for a pre-existing condition that had not worsened from baseline (e.g., elective or scheduled surgery arranged prior to start of the study).

This definition permits either the sponsor or the investigator to decide whether an event is “serious”. If either the sponsor or the investigator believes that the event is serious, the event must be considered “serious” and evaluated by the sponsor for expedited reporting.

8.3.8 Adverse Event Documentation

All AEs and SAEs occurring on Day 1 through the Day 29 (± 1 day)/Final Visit must be fully recorded in the subject’s medical record and CRF, and SAE form (if serious).

At the time of the Day 60 (± 2 days) and Day 90 (± 2 days) Phone Checks any additional SAEs/non-serious AEs will also be collected and recorded.

It is the responsibility of the investigator to ensure that AEs are appropriately recorded.

AEs will be collected through directly observed events or spontaneously volunteered by the subject. Clearly related signs, symptoms and abnormal diagnostic procedures should preferably be grouped together and recorded as a single diagnosis or syndrome wherever possible.

The following variables must be recorded:

- The verbatim term (a diagnosis is preferred)
- Date/time of onset
- Date/time of resolution
- Severity (mild, moderate, severe [Grade 3 to Grade 5])
- Causality (unrelated, possibly related, definitely related)*
- Seriousness (yes, no)
- Action taken (with regard to IP)
- Other action (to treat the event)
- Outcome and sequel (follow-up on AE)

*Causality assessment will be made only when the AE occurs after the subject has initiated at least one infusion of the IP. An AE occurring before subject’s exposure to IP will be always labeled as “unrelated”.

GRIFOLS Bioscience Industrial Group	Number	BlG-CL-PRT-000020	Version	4.0	Status	Effective	Effective Date	19-Jul-2021	Page	61 of 91
	GC2007 - A Multicenter, Randomized, Open-label Parallel Group Pilot Study to Evaluate Safety and Efficacy of High Dose Intravenous Immune Globulin (IVIG) plus Standard Medical Treatment (SMT) versus SMT alone in									

For AEs that occur during infusions, the infusion rate in effect at the time of onset of the AE, the time of onset of the AE and the time of AE change materially in intensity and/or resolve will be captured.

In addition to the investigator's own description of the AE, each AE will be encoded according to the Medical Dictionary for Regulatory Activities (MedDRA).

For example, a laboratory test abnormality considered clinically significant, e.g., causing the subject to withdraw from the study, requiring treatment or causing apparent clinical manifestations, or judged clinically significant in the context of the subject's medical history by the investigator, should be reported as an AE. Each event must be described in detail along with start and stop dates, severity, relationship to IP, action taken and outcome. Each event must be adequately supported by documentation as it appears in the subject's medical or case file.

8.3.9 Reporting of Serious Adverse Events

Any SAE (see Section 8.3.7) that occurs after informed consent on Day 1 through the Day 29 (± 1 day)/Final Clinic Visit and any SAE recorded at the time of the Day 60 (± 2 days) or Day 90 (± 2 days) Phone Checks must be fully recorded in the subject's medical record, CRF and SAE Report form. SAEs must be expeditiously reported whether or not considered attributable to the IP.

Serious adverse events will be reported using the designated SAE Report Form. When the investigator becomes aware of an SAE, she/he must submit a completed, signed and dated SAE Report Form (in English) **within 24 hours** to the sponsor by email/fax. The date of this SAE discovery by the site staff should be documented in the source documents (ie, medical records).

Each SAE must be followed up until resolution or stabilization. After the initial report, all relevant information for SAE follow-up, and for the outcome, must also be supplied to the sponsor in a timely manner (within 3 days from its identification or within 24 hours for relevant new information) by means of the SAE Report Form. In addition, the sponsor may request additional information and/or reports.

All SAE Report Forms must be reported to Grifols via email or fax as follows:

Grifols Global Pharmacovigilance
Email: [REDACTED]
FAX (back-up only): [REDACTED] (International)

When required, and according to local law and regulations, SAEs must be reported to the IRB/EC and regulatory authorities. Copies of the investigator's reports must be sent to the sponsor.

GRIFOLS Bioscience Industrial Group	Number	BLG-CL-PRT-000020	Version	4.0	Status	Effective	Effective Date	19-Jul-2021	Page	62 of 91
	GC2007 - A Multicenter, Randomized, Open-label Parallel Group Pilot Study to Evaluate Safety and Efficacy of High Dose Intravenous Immune Globulin (IVIG) plus Standard Medical Treatment (SMT) alone in									

8.4 Type and Duration of the Follow-Up of Subjects after Adverse Events

In so far as is possible, all individuals will be followed up until the AE or suspected ADR has been resolved. If an AE/suspected ADR/SAE is present when the subject has completed the study, the course of the event must be followed until the final outcome is known, or the event has been stabilized and no further change is expected and the investigator decides that no further follow-up is necessary.

8.5 Study-Independent Safety Review Committee (SISRC) and Stopping Rules

Grifols will utilize a Study-Independent Safety Review Committee (SISRC) whose members (from Grifols) will be impartial and independent of the clinical trial team, and will consist of a statistician, global pharmacovigilance representative, and medical director. The SISRC will review relevant safety information from the study as outlined in the SISRC Charter. At a minimum, after the first 20 subjects are enrolled and have completed treatment, the SISRC will conduct an initial safety review. The SISRC will perform a causality review of all TEAEs and SAEs. The SISRC will be notified of relevant SAEs inasmuch as feasible within 24 hours, but no later than 3 days.

Stopping criteria for temporary suspension of further study enrollment/recruitment pending full safety investigation by the SISRC are detailed below.

The SISRC will conduct a safety evaluation and study enrollment/recruitment will be temporarily suspended while the safety investigation is undertaken if any one of the following occur:

- 1 death considered related to Gamunex-C
- 1 Grade 4 treatment-emergent AE occurs in any of the first 3 randomized subjects considered potentially related to Gamunex-C
- 1 subject develops a Grade 3 hypersensitivity reaction or serious anaphylactic reaction at any time attributable to Gamunex-C
- 10 subjects given Gamunex-C develop treatment-emergent AEs in the same system organ class that are \geq Grade 2 severity (CTCAE grading criteria)
- 2 subjects given Gamunex-C develop treatment-emergent Grade 4 serious AEs of the same kind in the first 10 subjects randomized to Gamunex-C
- 5 subjects develop Grade 3 or 4 treatment-emergent AEs that are at least possibly related to Gamunex-C at any time during the study
- 3 or more subjects per 10 subjects enrolled and dosed with Gamunex-C develop definitely related treatment-emergent serious AEs of the same kind (same or related verbatim terms). This stopping criterion will be applied after at least 10 subjects are randomized and treated with Gamunex-C.

GRIFOLS	Number	BLG-CL-PPR-000020	Version	4.0	Status	Effective	Effective Date	19-Jul-2021
	GC2007 - A Multicenter, Randomized, Open-label Parallel Group Pilot Study to Evaluate Safety and Efficacy of High Dose Intravenous Immune Globulin (IVIG) plus Standard Medical Treatment (SMT) versus SMT alone in Bioscience Industrial Group						Page	63 of 91

- An unanticipated safety signal is detected by the SISRC that was unexpected and of sufficient magnitude to warrant concern

Further details are outlined in the SISRC Charter.

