4.2 Study Design and Plan

This is a prospective, multi-center, randomized (1:1), open-label, pilot study of high dose IVIG plus SMT versus SMT alone in subjects with COVID-19 who are hospitalized and require ICU admission. The first 6 subjects randomized will be staggered with an interval of no less than 1 week between subjects. If there are no definitely related serious adverse events (SAEs) reported 1 week after the randomization of the 6th subject, competitive enrollment would ensue thereafter. If a definitely related SAE were to be reported among these 6 subjects, the Study-Independent Safety Review Committee (SISRC) would carefully review and evaluate the case and make appropriate recommendations with regard to study status.

In this study, symptomatic subjects with positive polymerase chain reaction (PCR; reverse transcriptase [RT]-PCR) or other FDA-approved or regulatory-authority-approved diagnostic assay for SARS-CoV-2 in any specimen during the current hospital admission prior to randomization will receive SMT or SMT plus a net total dose of IVIG of 2 g/kg (body weight) administered in divided doses over 4 to 5 consecutive days at the Principal Investigator's discretion. The maximum dose will be capped at 160 g (equivalent to body weight of 80 kg).

Specifically, subjects randomized to combination high dose IVIG will receive the first IV infusion of IVIG on Day 1. The total net dose of 2 g/kg body (capped at a maximum of 160 g for subjects weighing more than 80 kg) will be administered in divided doses over consecutive days. At the discretion of the Principal Investigator, the 2 g/kg net total dose may be divided either into (a) infusions of 500 mg/kg body weight over 4 days OR (b) 400 mg/kg body weight over 5 days.

Approximately 100 subjects will be randomized (1:1) with an interim analysis after 50 subjects (approximately 25 per group). There will be no interruption in study conduct during interim analysis as this simply represents sponsor safety due diligence.

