4.3.2 Randomization

Subjects will be randomized 1:1 to receive either combination treatment with IVIG plus SMT or SMT alone. A central randomization will be used for this study. A randomization list containing the randomization numbers and the corresponding randomized treatment assignments will be generated by using a SAS program and be stored in a secured area that is only accessible to the randomization team. Once a subject has met eligibility criteria, a site personnel will email a randomization request to the randomization center. A randomization center operator will randomize the subject by selecting the next available randomization slot in the randomization list, starting at the top of the list and moving toward the bottom of the list, and reply to the email with the randomization number and corresponding randomized treatment assignment included. The personnel will communicate the randomization number, date/time, and treatment assigned to the site study staff, so that the information can be entered in the case report form.

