8.3.4 Assessment of Causality of Adverse Event

The investigator is required to provide a causality assessment for each AE reported to the sponsor. The assessment of the causal relationship of an AE to the administration of IP must be a clinical decision based on all available information at the time of the completion of the CRF and/or SAE Report Form. The sponsor will consider the investigator's causality assessment and also provide its own assessment.

Causal relationship to the IP will be established according to medical judgment on whether there is a **reasonable possibility of a causal relationship between the AE and the IP administration.**

The investigator must determine and classify the AE causality according to the following categories:

Unrelated/Not related: there is not a reasonable possibility of causal relationship between the AE and the IP.

Possibly related: there is evidence to suggest a causal relationship between the IP and the AE.

Definitely related: there is a reason to conclude that the IP caused the AE.

Criteria to assess the causal relationship should take into account of the following conditions: 1) a plausible temporal sequence from the IP administration to the AE onset; 2) whether the event follows a known response pattern to the suspected treatment; 3) whether the AE could be reasonably explained by the subject's clinical state, comorbidities, or concomitant medications, as well as 4) the occurrence of improvement on stopping/reducing the treatment (positive dechallenge) and/or reappearance of the event on repeated exposure (positive rechallenge).

For expedited safety reporting purposes, AEs assessed as either "definitely related" or "possibly related" will be considered POTENTIALLY RELATED or just RELATED.

Any AE reported prior to the first administration of the IP will be considered a non-treatment-emergent AEs and causal relationship will always be "Unrelated/Not related."

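### The Grade 4 stopping rule and the staggered start count randomised subjects of either arm, while other Section 8.5 rules count Gamunex-C subjects, so both early safeguards rest on few exposed subjects

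*Protocol*

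**What the plan says.** Two early safeguards are defined by order of randomisation, whatever the arm.

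- **Grade 4 rule (Protocol 8.5).** Enrolment is suspended for a safety investigation if "1 Grade 4 treatment-emergent AE occurs in any of the first 3 randomized subjects considered potentially related to Gamunex-C".
- **Staggered start (Protocol 4.2; repeated in the synopsis and SAP 3.1).** "The first 6 subjects randomized will be staggered with an interval of no less than 1 week between subjects". If no definitely related SAE is "reported 1 week after the randomization of the 6th subject, competitive enrollment would ensue thereafter". No minimum number on Gamunex-C is required for that release.

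On allocation, Protocol 4.3.2 states: "Subjects will be randomized 1:1 to receive either combination treatment with IVIG plus SMT or SMT alone". Subjects are assigned by "selecting the next available randomization slot in the randomization list". Neither that section nor SAP 3.2.1 gives a block size.

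On attribution, Protocol 8.3.8 states: "Causality assessment will be made only when the AE occurs after the subject has initiated at least one infusion of the IP". Events before exposure are always labelled unrelated.

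Elsewhere in Section 8.5 the count is of Gamunex-C subjects. The rule on two Grade 4 serious events of the same kind refers to the first 10 randomised to Gamunex-C. The rule on definitely related serious events counts subjects dosed with it and applies only once at least 10 have been treated. The system-organ-class rule counts subjects given it.

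**The concern.** Both safeguards look for harm attributed to Gamunex-C, but about half of the subjects who make up their counts will never receive it. Read quickly, the protocol seems to watch 3 and then 6 patients on high-dose IVIG before enrolment opens up. In fact it watches 3 and then 6 randomised patients, and the number exposed is left to the list. Section 8.5 itself shows that the authors could count by exposure when they wished, and no reason is given for counting differently here.

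At stake is how much early information on Gamunex-C exists when competitive enrolment starts, and whether the Grade 4 rule, which lapses after the third randomisation, has had anyone to act on.

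**Working it through.** The documents give no expected number exposed and no operating characteristics for these rules, so there is no figure of the plan's own to reproduce.

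**Inputs**
- Allocation 1:1, one central list used in order (Protocol 4.3.2).
- Counts of 3 (Protocol 8.5) and 6 (Protocol 4.2).
- Block size: not stated, so a range is assumed.
- Every subject randomised to Gamunex-C is taken as exposed. Any who never starts an infusion lowers the counts below.

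**Step 1: mean number exposed.** n × 0.5 gives 3 × 0.5 = 1.5 and 6 × 0.5 = 3, whatever the block size.

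**Step 2: unblocked allocation.** P(k of n) = C(n,k) × 0.5^n.
- First 3: P(0) = 1/8 = 12.5%; P(at most 1) = (1 + 3)/8 = 50%.
- First 6: P(0) = 1/64 = 1.6%; P(at most 1) = (1 + 6)/64 = 10.9%; P(at most 2) = (1 + 6 + 15)/64 = 34.4%.

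**Step 3: permuted blocks of size b.** Each complete block contributes b/2. For the r subjects in the incomplete block, P(k) = C(b/2,k) × C(b/2,r−k) / C(b,r). Two examples:
- Blocks of 4, first 6: 2 from the full block, then r = 2, so P(total 2) = C(2,0) × C(2,2) / C(4,2) = 1/6 = 16.7%.
- Blocks of 6, first 3: P(0) = C(3,0) × C(3,3) / C(6,3) = 1/20 = 5.0%.

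| Allocation (assumed) | Exposed among first 3 | Exposed among first 6 |
|---|---|---|
| Unblocked | 0 to 3; none 12.5% | 0 to 6; none 1.6%, at most 1 10.9% |
| Blocks of 2 | 1 or 2 | exactly 3 |
| Blocks of 4 | 1 or 2 | 2 to 4; two 16.7% |
| Blocks of 6 | 0 to 3; none 5.0% | exactly 3 |
| Blocks of 8 | 0 to 3; none 7.1% | 2 to 4; two 21.4% |
| Blocks of 10 | 0 to 3; none 8.3% | 1 to 5; one 2.4% |
| One block of 100 | 0 to 3; none 12.1% | 0 to 6; none 1.3%, at most 1 10.2% |

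**Step 4: chance that a rule sees at least one event.** Let p be the rate, per exposed subject, of the event that the rule looks for. The documents give no such rate, so p is assumed at 5% to 30%. Under unblocked allocation a count of n randomised gives 1 − (1 − p/2)^n; a count of n exposed gives 1 − (1 − p)^n.

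| p (assumed) | 3 randomised | 3 exposed | 6 randomised | 6 exposed |
|---|---|---|---|---|
| 5% | 7.3% | 14.3% | 14.1% | 26.5% |
| 10% | 14.3% | 27.1% | 26.5% | 46.9% |
| 20% | 27.1% | 48.8% | 46.9% | 73.8% |
| 30% | 38.6% | 65.7% | 62.3% | 88.2% |

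**Step 5: calendar time.** Five intervals of at least one week, plus one week after the sixth randomisation, give at least 6 weeks from first randomisation to release.

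**The case against.** Exposed subjects are not left without protection. Under Section 8.5 a related death, or a Grade 3 hypersensitivity or serious anaphylactic reaction attributable to Gamunex-C, suspends enrolment at any time. So do five subjects with at least possibly related Grade 3 or 4 events, or an unexpected signal of concern. The SISRC reviews causality of all TEAEs and SAEs. The product is licensed, with more than 8 million estimated infusions (Protocol 2.2), so this is not a first-in-human setting. The SISRC Charter and the randomisation specification are not among the documents and might fix a block size or a minimum number exposed. All of this stands. It limits the consequence but does not explain the mixed denominators.

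Three stronger readings are tempting and not supported.

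- **That enrolment may well open with nobody exposed.** For the first 6 this has probability at most 1.6%, and it is impossible with fixed blocks of 10 or smaller. The point about the 6-subject gate is few exposed, not none.
- **That the definitely-related test in Section 4.2 contradicts Section 8.3.4**, where possibly and definitely related events "will be considered POTENTIALLY RELATED or just RELATED". That sentence is limited to expedited safety reporting, and Section 8.5 sets its causality threshold rule by rule. A different threshold in Section 4.2 is a choice, not an inconsistency.
- **That the weeks after SMT-alone subjects are wasted and could be dropped.** They lengthen follow-up of subjects already exposed and are part of the 6-week minimum. Removing them would shorten that minimum.

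**Conclusion.** The concern holds as an inconsistency of denominator. The Grade 4 rule and the staggered start count both arms; other rules in Section 8.5 count Gamunex-C subjects; and SMT-alone subjects cannot trigger either early safeguard. The average of 1.5 exposed among the first 3 and 3 among the first 6 follows from 1:1 allocation alone.

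The spread depends on a block size that the documents do not state. The 12.5% (none of the first 3) and 11% (at most 1 of the first 6) belong to unblocked allocation, at the unfavourable end of the range. They should not be read as properties of the actual list, because leaving out a block size does not show that there is no blocking. With blocks of 4 the first 3 hold 1 or 2 and the first 6 hold 2 to 4.

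This is worth correcting because it concerns early patient safety and needs only wording. It does not show that exposed subjects go unmonitored.

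**What to change.** Reconcile the denominators in the synopsis, Protocol 4.2 and 8.5, and SAP 3.1.

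1. Express the Grade 4 rule in subjects given Gamunex-C, as other rules in Section 8.5 do.
2. Keep the 6-subject, one-week stagger, and add a minimum number of Gamunex-C-exposed subjects before competitive enrolment opens. The sponsor and the SISRC should set that number. If the Charter or the randomisation specification already secures one, the protocol should say so.

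**Cost.** The stagger would be extended only when the first 6 fall short of the minimum, by at least a week per further subject. For illustration, a minimum of 2 would not be met by the sixth subject in 10.9% of unblocked lists and never with blocks of 4. A minimum of 3 would not be met in 34.4% and 16.7% respectively, and would always be met with blocks of 2 or 6. Large minimums are expensive: 6 exposed would need 6/0.5 = 12 randomisations on average. The revised Grade 4 rule would stay active for longer (3/0.5 = 6 randomisations on average), so a temporary suspension becomes somewhat more likely, as step 4 shows. The planned total of about 100 subjects need not change.

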4.1.4 Safety Endpoints

The safety endpoints include:

- Cumulative incidence of treatment-emergent serious adverse events (SAEs) and potentially related SAEs through Day 90 Phone Check
- Cumulative incidence of Grade 3-5 treatment-emergent adverse events (TEAEs) and potentially related severe TEAEs through Day 29 as defined in the Common Terminology Criteria for Adverse Events (CTCAE), US Department of Health and Human Services, National Institutes of Health (NIH), and National Cancer Institute (NCI)
- Cumulative incidence of all TEAEs and potentially related TEAEs through Day 29

GRIFOLS Bioscience Industrial Group	Number	BLG-CL-PRT-000020	Version	4.0	Status	Effective	Effective Date	19-Jul-2021	Page	33 of 91
	GC2007 - A Multicenter, Randomized, Open-label Parallel Group Pilot Study to Evaluate Safety and Efficacy of High Dose Intravenous Immune Globulin (IVIG) plus Standard Medical Treatment (SMT) versus SMT alone in									

In this clinical study, disease progression is defined as the worsening of a subject's condition attributable to the disease for which the investigational product is being studied. It may be an increase in the severity of the targeted disease and/or increases in the symptoms of the targeted disease. Anticipated symptoms of COVID-19 include fever, cough, hypoxia, dyspnea, hemoptysis, myalgia, fatigue, pharyngitis, which may develop at any time during the course of the disease. The development of COVID-19 symptoms during the clinical study should not be recorded as individual TEAEs, unless there is evidence suggesting a causal relationship between IVIG and the TEAE.

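### Five suspension triggers and the Grade 3-5 safety endpoint rely on CTCAE grades, but the protocol requires a grade only for events already called severe on a normal-activities scale, and neither document defines Grade 2

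*Protocol*

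**What the plan says.** **How events are rated.** Protocol 8.3.5 puts each adverse event into one of three classes by its effect on daily function. Two of them read "Moderate: an AE that interferes with the subject's normal activities" and "Severe: an AE that prevents the subject from performing their normal activities". CTCAE appears only under the severe class: "This category is further subdivided into Grade 3-5 AEs defined according to CTCAE criteria". Protocol 8.3.8 lists the variables that sites must record, and the entry here is "Severity (mild, moderate, severe [Grade 3 to Grade 5", with the grades in brackets after severe only. SAP 7.2.2 has no rule of its own and points back to Protocol 8.3.5.

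**How grades are used.** Protocol 8.5 has eight triggers for suspending enrolment. One applies when "10 subjects given Gamunex-C develop treatment-emergent AEs in the same system organ class that are" Grade 2 or worse, and the same bullet names CTCAE as the grading system. Others include "2 subjects given Gamunex-C develop treatment-emergent Grade 4 serious AEs of the same kind in the first 10 subjects randomized to Gamunex-C" and "5 subjects develop Grade 3 or 4 treatment-emergent AEs that are at least possibly related to Gamunex-C at any time during the study". Protocol 4.1.4 has the safety endpoint "Cumulative incidence of Grade 3-5 treatment-emergent adverse events (TEAEs) and potentially related severe TEAEs through Day 29", defined by CTCAE. SAP 7.2.5 tabulates treatment-emergent events and adverse drug reactions of Grade 3 or higher.

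**The concern.** The rules that use grades and the rules that create them do not match. A trigger set at CTCAE Grade 2 needs someone to decide which events are Grade 2, but the rating text assigns no grade below 3. For Grade 3 and above, the text makes the functional label come first: an event is called severe and only then graded. An event that CTCAE would place at Grade 3, but that the investigator calls moderate, leaves the site with no instruction to grade it.

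The functional scale also suits this population poorly. Subjects need ICU-level care and are on supplemental oxygen, mechanical ventilation or both, so interference with normal activities separates events badly. It suits laboratory findings no better. Protocol 8.3.8 requires clinically significant laboratory abnormalities to be reported as adverse events, and Protocol 2.3.2 lists acute renal failure and haemolysis among the main risks of the product. Those are events where a laboratory value may say more than function does.

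At stake are whether the suspension triggers can be counted in the way 8.5 describes, and whether the Grade 3-5 endpoint measures what its name says. The trial is open-label, so the label that decides whether an event is graded is given by someone who knows the arm.

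**Working it through.** **1. No plan figure to reproduce.** The documents give no adverse event rates and no operating characteristics for the triggers. The check is therefore a comparison of texts, followed by an illustration.

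**2. Each use of a grade against what is recorded.**

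| Use | Place | Grade needed | Supplied by 8.3.5 and 8.3.8? |
|---|---|---|---|
| Potentially related event in any of the first 3 randomized | Protocol 8.5 | 4 | Only if called severe |
| Hypersensitivity reaction in 1 subject | Protocol 8.5 | 3 | Only if called severe |
| 10 subjects, one organ class | Protocol 8.5 | 2 or higher | Grade 2 not defined; Grade 3 or higher only if called severe |
| 2 subjects among the first 10 on Gamunex-C, serious, same kind | Protocol 8.5 | 4 | Only if called severe |
| 5 subjects, at least possibly related | Protocol 8.5 | 3 or 4 | Only if called severe |
| Safety endpoint | Protocol 4.1.4 and 8.1, SAP 2.2.4 | 3 to 5 | Only if called severe |
| Event and drug-reaction tables | SAP 7.2.5 | 3 or higher | Only if called severe |

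The other three triggers (a related death, definitely related serious events of one kind, an unexpected signal) use no grade. So 8 − 3 = 5 triggers rely on grades: the Grade 2 rule and four stated in Grade 3 and/or 4.

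**3. One event followed through.** Suppose a creatinine rise is judged clinically significant and reported. The investigator rates it on normal activities and calls it moderate. The required record then holds moderate and no grade. If CTCAE would make it Grade 2, it belongs in the organ-class count and has nothing to enter it by. If CTCAE would make it Grade 3, it also belongs in the endpoint, in the SAP table and, if related, in the five-subject count, and it has no grade for any of them.

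**4. Illustration of what under-identification could do.** The rates and shares below are assumptions.

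- Subjects on Gamunex-C: about 100 randomized 1:1, so n = 100/2 = 50.
- True proportion of subjects with a qualifying event: p. Share of them identified: s. Effective rate: q = p × s.
- P(at least r of n) = Σ C(n,k) q^k (1 − q)^(n − k), summed over k from r to n.

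| Rule | p | s = 1 | s = 0.75 | s = 0.5 |
|---|---|---|---|---|
| 10 of 50, Grade 2 or higher, one organ class | 20% | 0.556 | 0.209 | 0.025 |
| | 30% | 0.960 | 0.716 | 0.209 |
| | 40% | 0.999 | 0.960 | 0.556 |
| 5 of 50, related Grade 3 or 4 | 10% | 0.569 | 0.320 | 0.104 |
| | 15% | 0.888 | 0.676 | 0.320 |
| | 20% | 0.982 | 0.888 | 0.569 |

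For example, p = 30% and s = 0.5 give q = 15% and P(at least 10 of 50) = 0.209. The first rule is computed for a single organ class, while the protocol applies it to any class. The table shows how sensitive a count is to missed subjects. It does not estimate how many would be missed.

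**The case against.** A reader might infer more: that Grade 2 events will never be identified, that every mild or moderate event lacks a grade, or that renal and haemolytic signals will be lost. The documents do not support this, for four reasons.

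- **A grade may be collected.** The adverse event listing in SAP 7.2.5 names grade as an item separate from severity, and the SAP summarises greatest severity and Grade 3 or higher separately. The eCRF and the SISRC Charter were not supplied, and either may cover part of the gap.
- **The severe gate is not stated everywhere.** Footnote d of the schedule of procedures, like the endpoint text, says that Grade 3-5 events are defined by CTCAE and sets no functional precondition. The bracket in 8.3.8 can be read as equating severe with Grades 3 to 5, which would leave moderate as Grade 2.
- **The population is mixed.** Supplemental oxygen alone meets the inclusion criterion, and events are also recorded after discharge. Investigators can use the moderate class, so they are not forced to choose between severe and mild.
- **There are other safeguards.** Laboratory values are summarised by visit, with shift tables where ranges exist. Serious events are reported whatever their grade. The SISRC reviews causality for all events and has a trigger for any unexpected signal.

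All four stand as limits on the claim. None closes the gap. The SAP item is undefined, and SAP 7.2.2 sends severity back to 8.3.5. Footnote d does not mention Grades 1 and 2. Reading moderate as Grade 2 is a guess that neither document states. A charter can tell a committee how to review records, but it does not by itself make sites record a grade.

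**Conclusion.** The point holds as a conflict between stated rules. As written, the Grade 2 trigger has no defined input. The four triggers stated in Grade 3 and/or 4, the CTCAE endpoint and the SAP tables depend on a grade that is required only after a non-CTCAE functional judgement. An event meeting CTCAE Grade 3 can therefore go ungraded if it is called moderate.

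The size of the effect is unknown. The illustration shows that missing half the qualifying subjects would matter to either count (0.960 to 0.209 at 30%, and 0.888 to 0.320 at 15%), but the rates and the share of one half are assumptions, and the documents cannot supply real ones. The conclusion rests on the protocol and SAP alone. If the eCRF already holds a CTCAE grade for every event, what remains is to say so in the text. This should be corrected because the change is cheap and the triggers protect subjects. It does not show that any safety signal has been or will be lost.

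**What to change.** - In Protocol 8.3.5 and 8.3.8, require a CTCAE grade from 1 to 5 for every adverse event in both arms, and name the CTCAE version. Have it assigned independently of the mild, moderate or severe label. The functional label may stay as a separate variable, but should not decide whether an event is graded.
- In SAP 7.2.2 and 7.2.5, define the listing's grade item as this field, and produce the Grade 3 or higher tables from it.
- In Protocol 8.5, state that all grade-based counts use this field. Leave the thresholds as they are.

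**Cost.** A few sentences in each document, an eCRF field if none exists, and retrospective grading of events already recorded without a grade. No extra visits or tests are needed.
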